## 2 TRIAL OBJECTIVES AND ENDPOINTS

### 2.1 Primary Objective

The primary objective of this pivotal study is to demonstrate that AMPLEX is non-inferior to ABG for bone fusion in a population indicated for single, double, or triple hindfoot arthrodesis or ankle arthrodesis surgery with supplemental graft material.

### 2.2 Endpoints

#### 2.2.1 Primary Efficacy Endpoint

The primary efficacy endpoint is the proportion of subjects who meet all the following criteria for the Subject Performance Composite (SPC) Endpoint at 52 weeks:

- Improvement in pain on weight-bearing at fusion site ( $\geq 20$  mm reduction from baseline on 100 mm VAS)
- Absence of significant graft harvest site pain ( $< 20$  mm on 100 mm VAS)
- Improvement in Foot and Ankle Ability Measure Activities of Daily Living subscale (FAAM-ADL) ( $\geq 8$  points improvement from baseline)
- Absence of device related or procedure related SAEs (up to Week 52)
- Absence of secondary surgical or nonsurgical interventions intended to promote fusion (up to Week 52)

#### 2.2.2 Secondary Endpoints

The key secondary endpoint is the proportion of subjects achieving CT radiographic fusion success at 52 weeks:

- Radiographic evidence of fusion by CT scan ( $\geq 50\%$  bone bridging across the joint space for the full complement of joints in the absence of secondary surgical or nonsurgical interventions intended to promote fusion)

The other secondary endpoints are as follows:

- Proportion of subjects achieving CT radiographic fusion success at 12 and 24 weeks (in the absence of secondary surgical or nonsurgical interventions intended to promote fusion)
- Change from baseline in pain on weight-bearing at fusion site at 12, 24, and 52 weeks ( $\geq 20$  mm reduction from baseline on 100 mm VAS)
- ABG harvest site pain at 2, 6, 12, 24, and 52 weeks ( $< 20$  mm on 100 mm VAS)
- Change from baseline in FAAM-ADL at 12, 24 and 52 weeks
- SPC at 12 and 24 weeks
- Change from baseline in Short Form-12 (SF-12) at 24 and 52 weeks

### **2.2.3 Safety Endpoints**

The safety endpoints are as follows:

- Frequency, severity and seriousness of Adverse Events (AEs)
- Device or Procedure Related SAEs
- Secondary surgical intervention including revision, removal, reoperation or supplemental fixation
- Subsidence, device migration, nonunion, osteolysis and/or heterotopic ossification in the area surrounding the implant site by radiographic assessment
- Presence of anti-B2A antibodies (Ab) in serum

### **2.2.4 Pharmacokinetic Endpoints**

- Plasma B2A levels at Days 1, 2, 4, 7, and 15
- Plasma AUC, AUCt, Cmax, Tmax, t1/2, CL/F, Vz/F for B2A

### 3 INVESTIGATIONAL PLAN

#### 3.1 Overall Trial Design

##### 3.1.1 Trial Design Diagram

[figure not shown]

Figure 1 Trial Design Diagram

##### 3.1.2 Trial Schedule

Investigational Device Exemption (IDE) Approval: 20 November 2015  
 Study Start-up: 6 months

Subject Enrollment: 18 months

Treatment and Follow-up: 18 months

Study Closeout: 4 months

**Total Duration: 46 months**

### **3.2 Planned Number of Trial Sites and Subjects**

The study will be conducted at up to a total of 50 centers; 35-40 US centers and 10-15 Canadian centers, following approval by appropriate oversight committees and regulatory agencies [Institutional Review Board (IRB) and Food and Drug Administration, USA (FDA) or the local Research Ethics Board (REB) and Health Canada, respectively] with informed consent obtained from all subjects.

Approximately 480 subjects will be randomized in a 2:1 ratio (Treatment: Control) with approximately 320 to receive AMPLEX and 160 to receive ABG.

### **3.3 Study Oversight**

#### **3.3.1 Clinical Events Committee**

An independent group of physicians that are not involved in the clinical investigations will act as the Clinical Events Committee (CEC). The CEC will be responsible for the review and adjudication of Investigator-reported events and events identified in the monitoring process. Any potential device, ancillary device or procedural related AEs, all events associated with secondary surgical intervention, and any other AEs specified in the CEC Charter will be adjudicated. Subsequent to Investigator determination of severity and relatedness of the event, the CEC shall classify each of these adverse events based on severity and association to the device and/or procedure. During the review of the events, the CEC will be blinded to the clinical site and treatment. The CEC Charter will be developed upon identification of committee members and shall include consistent definitions for each type of event and shall outline the review process.

#### **3.3.2 Data Monitoring Committee**

An independent panel of medical and biostatistics experts will serve in the capacity of Data Monitoring Committee (DMC). The DMC will periodically review clinical study data to ensure patient safety, trial integrity, and scientific rigor. DMC members will have relevant orthopedic experience and medical knowledge of the product under investigation. The DMC will develop and ratify a Charter that provides guidelines for oversight of trial safety. The Charter will define the scope and DMC's responsibilities, quorum, operating guidelines, sample template for required data analyses, pre-defined stopping rules, communication pathway to the study Sponsor, and frequency of meetings.

### **3.3.3 Imaging Core Laboratory**

An independent imaging core laboratory will be utilized for assessment of radiographic images at each follow-up visit in which a radiographic image is obtained. A comprehensive description of the imaging methodology will be detailed in an imaging core lab Radiographic Evaluation Protocol (REP) provided in the Site Reference Manual (SRM). All radiographic imaging shall be performed in accordance with this protocol.

Prior to development of the REP, the imaging core laboratory conducted a Radiographic Image Review and Validation Assessment to determine the impact of any potential confounding factor (i.e., metallic screws in the graft site, radio-opacity of the graft material) on the ability of readability of the images and utilized the information to develop the REP.

The assessment of fusion status and device condition shall be performed by an independent imaging core lab in compliance with their REP provided in the SRM. Results of these assessments will not be adjudicated by the CEC,

## **3.4 Discussion of Overall Trial Design and Choice of Control Groups**

### **3.4.1 Trial Design**

This is a prospective, multi-center clinical trial in subjects ( $\geq 18$  and  $< 75$  years of age) undergoing tibiotalar (ankle) arthrodesis or single, double, or triple hindfoot (talocalcaneal-, calcaneocuboid- or talonavicular-joint) arthrodesis with supplemental graft material and internal fixation with up to 3 screws per joint.

Subjects will be followed for 78 weeks. Post-discharge clinical visits will include visits at 2, 6, 12, 24, 52 and 78 weeks. Adverse event data will be collected throughout the study. The primary endpoint will be assessed at 52 weeks.

The objective of the trial is to demonstrate that AMPLEX is non-inferior to ABG for bone fusion in a population indicated for ankle arthrodesis or single, double, or triple hindfoot arthrodesis surgery with supplemental graft material. The study will be declared successful if non-inferiority of AMPLEX compared to ABG in the primary efficacy endpoint is demonstrated in the mITT analysis population within a non-inferiority margin of -12.0% at a type I error rate of 1-sided 5%.

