**OBJECTIVE**

To demonstrate that AMPLEX is non-inferior to autogenous bone graft (ABG) for bone fusion in a population indicated for single, double, or triple hindfoot arthrodesis or ankle arthrodesis surgery with supplemental graft material.

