### **1.4 Clinical Benefit**

The proposed clinical study is designed to demonstrate that AMPLEX is non-inferior to ABG for bone fusion in a population indicated for single, double, or triple hindfoot arthrodesis or ankle arthrodesis surgery with supplemental graft material. The potential benefit to AMPLEX subjects is successful fusion of the ankle or hindfoot via an operation that is smaller in magnitude and devoid of the risks and additional pain associated with the harvesting of autogenous bone graft. Subjects who receive AMPLEX may experience the following potential benefits:

1. Similar rate of fusion compared to autograft without the additional risks of the autograft procedure (i.e., harvest site pain, longer anesthetic and longer procedure, harvest site infection, harvest site fracture, or other complications)
2. Higher rate of fusion compared to autograft without the additional risks of the autograft procedure
3. Similar or higher rate of fusion at earlier time points than autograft without the additional risks of the autograft procedure
4. Similar or larger extent of fusion as measured by trabecular bridging of bone across the fusion site.

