CT imaging is logistically feasible, is a meaningful endpoint and has been used in past FDA studies. It reflects the proposed benefit of the therapies, the underlying clinical condition and has precedence for use. Its use is also independent of the assigned randomization and would therefore represent an objective measure of efficacy. Consistent interpretation in these complex anatomies is important in obtaining unbiased assessments, supporting the use of an independent imaging core lab with expertise in this area for image interpretation. The blinding of radiographic reviewers from clinical information further adds to the validity of the assessments. Although there may be radiographic differences observed in the treatments, the blinding of the reviewers in this trial is consistent with the current draft guidance on imaging in clinical trials.

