Surgeries will be performed by board-certified/board eligible orthopedic surgeons. Perioperative prophylactic antibiotics will be administered before surgical incision in accordance with investigational site guidelines. Standard anesthesia procedures will be used. Standard surgical technique will be employed to gain access to each fusion site and to ensure rigid fixation of the fusion site. The joint will be exposed and prepared as per standard practice. The graft material should be placed in the joint space to minimize the chance of extrusion while maximizing bone-on-bone contact. Once the graft is placed, internal fixation screws will be placed across the joint. Up to three (3) screws can be used per joint. Supplemental pins and staples may be used, as well as supplemental screws and plates external to the fusion site(s). The surgical site will be closed in layers using standard surgical technique.

The trial is designed as a randomized, controlled trial comparing AMPLEX to ABG for bone fusion at 52 weeks. Although the primary efficacy endpoint will be assessed at 52 weeks, all subjects will be followed up for 78 weeks for the safety assessment. Post-discharge clinical visits will include

visits at 2, 6, 12, 24, 52 and 78 weeks. Adverse event data will be collected from randomization until the final follow up. The schedule of assessments is described in [Appendix 3](#).

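### The primary objective is worded as non-inferiority for bone fusion, but study success rests on the clinical composite alone, and nothing ties that objective to the CT fusion test

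*Protocol*

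**What the plan says.** The bone-fusion wording runs through both documents:

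- Protocol Synopsis, Objective: "To demonstrate that AMPLEX is non-inferior to autogenous bone graft (ABG) for bone fusion".
- Protocol 1.4: "The proposed clinical study is designed to demonstrate that AMPLEX is non-inferior to ABG for bone fusion".
- Protocol 2.1 gives the primary objective as to "demonstrate that AMPLEX is non-inferior to ABG for bone fusion"; SAP 2.1 repeats it.
- SAP 3: "The trial is designed as a randomized, controlled trial comparing AMPLEX to ABG for bone fusion at 52 weeks".
- Protocol 3.4.1: "The objective of the trial is to demonstrate that AMPLEX is non-inferior to ABG for bone fusion".

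The next sentence of Protocol 3.4.1 sets the success rule: "The study will be declared successful if non-inferiority of AMPLEX compared to ABG in the primary efficacy endpoint is demonstrated". It applies in the mITT set, with a margin of -12% and a one-sided 5% level.

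The primary endpoint (Protocol 2.2.1, SAP 2.2.1) is SPC success at 52 weeks. Its five items are weight-bearing pain, harvest-site pain, FAAM-ADL, device- or procedure-related SAEs, and interventions intended to promote fusion. CT radiographic fusion at 52 weeks is the key secondary endpoint. It is second in the fixed sequence (Protocol 9.6.1, SAP 9.1), and SAP 9.3.1 gives it its own claim rule with the same margin and confidence level.

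**The concern.** The stated objective and the success rule concern different quantities. The only SPC item connected with fusion is the absence of interventions meant to promote it, and that item is indirect. A subject with a nonunion that is not re-treated, whose pain and function improve and who meets the other items, is an SPC success.

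The protocol itself treats the two ideas as separate. Section 3.4.2 justifies the SPC as an assessment of benefit and risk, and says of CT imaging: "It reflects the proposed benefit of the therapies, the underlying clinical condition and has precedence for use". Section 1.4 lists as a benefit in its own right: "Similar rate of fusion compared to autograft without the additional risks of the autograft procedure".

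Meeting the primary endpoint is normally read as meeting the primary objective. On the present wording, a trial that passes on the SPC and fails on CT fusion could be reported as having met a bone-fusion objective.

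**Working it through.** **Text.** No section of either document says that study success, or the bone-fusion objective, depends on the CT test. That absence is the finding. The arithmetic below only shows how often the two results could part.

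**Inputs (Protocol 9.1).** SPC success 60% ABG and 62% AMPLEX; CT fusion 70% to 75%, equal in both arms; margin 0.12; one-sided 5% (z = 1.645); 264 AMPLEX and 132 ABG evaluable; 320 and 160 randomized.

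**Formula.** Power = Φ[(0.12 + pA - pB)/SE - 1.645], with SE = √[pA(1 - pA)/nA + pB(1 - pB)/nB], where A is AMPLEX and B is ABG.

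**Reproducing the plan's figures at 264/132.**

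- Test 1 (SPC): SE = √(0.2356/264 + 0.24/132) = 0.0521; 0.14/0.0521 - 1.645 = 1.044; power 85.2%. The plan says 85% with 396 subjects.
- Test 2 (CT at 70%): SE = √[0.21 × (1/264 + 1/132)] = 0.0489; power 79.1%.
- Test 2 (CT at 75%): SE = √[0.1875 × (1/264 + 1/132)] = 0.0462; power 83.0%. The plan says 79% to 83%.

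The sample size is therefore correct for what it targets, which is the SPC.

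**Both tests together, if independent.** Joint power is P1 × P2; test 1 passing with test 2 failing is P1 × (1 - P2).

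| Subjects | CT rate | Test 1 | Test 2 | Both pass | Test 1 passes, test 2 fails |
|---|---|---|---|---|---|
| 264/132 | 70% | 0.852 | 0.791 | 0.674 | 0.178 |
| 264/132 | 75% | 0.852 | 0.830 | 0.707 | 0.145 |
| 320/160 | 70% | 0.906 | 0.855 | 0.775 | 0.131 |
| 320/160 | 75% | 0.906 | 0.888 | 0.805 | 0.101 |

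The 320/160 rows are a ceiling. They assume that every randomized subject has surgery and that outcomes carried forward follow the planning rates.

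**Dependence.** The documents give no correlation between the tests. With an assumed correlation of 0.2 to 0.6 between the test statistics, the last column becomes 10-16% at 264/132 and 7-12% at 320/160. Under maximal positive dependence it is P1 - P2, that is 2-6% and 2-5%.

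**If AMPLEX fuses less well.** Assume true CT fusion is 12 points lower on AMPLEX. Then pA - pB = -0.12, the first term in the formula is zero, and test 2 passes with probability Φ(-1.645) = 5%. The success rule does not use this result. If the SPC rates stayed at their planning values, success would still be declared 85% of the time at 264/132. Poorer fusion may lower the SPC through pain, function or re-intervention, but the documents give no figure for that link.

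**The case against.** The operating rules are not ambiguous. The primary endpoint, the success rule, the test order and the CT claim rule agree across both documents, so two analysts would run the same tests and reach the same study verdict. The choice of a clinical composite is argued openly (Protocol 1.3 and 3.4.2), and the CT power is disclosed in Protocol 9.1. A claim on the CT endpoint already requires test 2. The phrase about bone fusion could also be read as naming what the graft is used for.

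Most of this stands, and it limits the point to the wording of the objective and the conclusion drawn from it. The last reading is weak, because Protocol 1.4 lists the fusion rate as a benefit and SAP 3 describes a comparison for fusion at 52 weeks.

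A reader might go further and infer that the ABG-only failure routes (harvest-site pain and harvest-procedure SAEs) make the SPC margin too lenient. The documents do not support that. Protocol 9.1 discloses the expected harvest-pain advantage and justifies -12% for the whole composite, citing the benefit of avoiding ABG risks; the margin cannot be carried over to part of the composite. No rate of harvest-related SPC failure is given: Protocol 1.1 cites 18% persistent harvest pain up to one year, but does not say that it matches the SPC criterion. AMPLEX-specific device-related SAEs, for which Protocol 1.5 lists risks, would act the other way. SAP 9.2.1 already summarises each SPC component.

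**Conclusion.** The inconsistency is real and should be corrected. The objective says bone fusion, success is decided on the SPC, and no text makes the bone-fusion objective conditional on test 2.

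Its scale at the planning rates, with equal true CT fusion and independent tests, is a 14-18% chance at 264/132 (10-13% at 320/160) that the SPC test passes and the CT test fails. A reader might take this as the frequency of false fusion claims. It is not: AMPLEX is truly non-inferior for fusion in that scenario, and the split comes from test 2's limited power. The case that matters for a wrong conclusion is lower true fusion on AMPLEX, where success would still depend on the SPC alone.

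Nor do the documents support reading this as a flaw in the primary test, the sample size or the choice of the SPC, or as a reason to make CT fusion co-primary. The plan's numbers reproduce, and the SPC is defended as a benefit/risk endpoint.

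**What to change.** In the Protocol Synopsis, Protocol 1.4, 2.1 and 3.4.1, and SAP 2.1 and 3, state the primary objective as non-inferiority of AMPLEX to ABG in SPC success at 52 weeks, and add:

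> Non-inferiority for bone fusion will be concluded only if test 2 (CT radiographic fusion at 52 weeks) of the fixed sequence is also passed.

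The success rule, N, alpha, margin and 85% power for the SPC are unchanged, and no new data are needed.

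The cost is a protocol amendment (Protocol 12.1) with a matching SAP revision. A bone-fusion conclusion will then need both tests, with joint power of about 67-71% at 264/132 or 77-80% at 320/160 if they are independent. The fixed sequence already imposes that condition on any CT fusion claim, so the new sentence only extends it to the wording of the objective.

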### 3.4.2 Selection of Endpoints

The primary endpoint of this trial is the success in the SPC, which consists of improvement in pain on weight bearing at fusion site, absence of significant graft harvest site pain, functional improvement, absence of device related SAEs or procedure related SAEs and absence of secondary surgical or non-surgical interventions intended to promote fusion. This endpoint is considered to provide relevant assessment to determine the benefit/risk profile of the investigational device (AMPLEX) compared to the control material (ABG) used in arthrodesis surgery involving hindfoot or ankle.

Functional improvement will be measured by the FAAM-ADL. It is a reliable and valid self-assessment instrument that was specifically developed to measure physical function for subjects with foot and ankle disorders (Martin, Irrgang, Burdett, Conti, & van Swearingen, 2005). The validity evidence for test content, internal structure, score stability, and responsiveness was demonstrated in 243 subjects including 51 (21%) subjects who underwent foot and ankle related surgery (Martin, Irrgang, Burdett, Conti, & van Swearingen, 2005). The reliability and responsiveness were further demonstrated in 311 subjects who underwent elective surgery for a foot or ankle related disorder (Hung, Baumhauer, Brodsky, & al., 2014). The minimal detectable change (MDC) and minimal clinically important difference (MCID) were identified as 5.7 and 8 points (Martin, Irrgang, Burdett, Conti, & van Swearingen, 2005).

Both harvest site pain and pain on weight bearing at fusion site will be measured by the 100 mm VAS. The 100mm VAS is a reliable self-assessment instrument commonly used in the assessment of pain. The VAS has been widely used in the clinical arena and research setting (Hawker, Mian, Kendzerska, & French, 2011) and is frequently employed in patients with musculoskeletal disorders (Tubach, et al., 2012). Minimal clinically important improvement in pain has been reported for knee and hip osteoarthritis at 19.9 mm and 15.3 mm respectively (Tubach, et al., 2005, p. 31). Additionally, improvement in baseline weight-bearing pain of >20 mm has been used as a component of a subject performance composite endpoint in other studies of ankle and hindfoot fusion. (FDA Orthopaedic and Rehabilitation Devices Division, 2011 [May]) (Daniels, et al., 2015, pp. 743-746) (Baumhauer J. et al, 2014, p. 107).

CT imaging is logistically feasible, is a meaningful endpoint and has been used in past FDA studies. It reflects the proposed benefit of the therapies, the underlying clinical condition and has precedence for use. Its use is also independent of the assigned randomization and would therefore represent an objective measure of efficacy. Consistent interpretation in these complex anatomies is important in obtaining unbiased assessments, supporting the use of an independent imaging core lab with expertise in this area for image interpretation. The blinding of radiographic reviewers from clinical information further adds to the validity of the assessments. Although there may be radiographic differences observed in the treatments, the blinding of the reviewers in this trial is consistent with the current draft guidance on imaging in clinical trials.

### **3.4.4 Trial Population**

Subjects will be  $\geq 18$  and  $< 75$  years of age and candidates for tibiotalar (ankle) arthrodesis or single, double, or triple hindfoot (talocalcaneal-, calcaneocuboid- or talonavicular-joint) arthrodesis with supplemental graft material. Subjects shall be screened prior to randomization to ensure they meet inclusion/exclusion criteria. The screening will include a review of all imaging and critical comorbid risk factors for nonunion by the Investigator.

A Pharmacokinetic (PK) assessment will be conducted in a sub-set of subjects to assess the amount of B2A in blood (plasma) after surgery, on Days 1, 2, 4, 7, and 15, and will include a baseline, pre-procedure evaluation. The sub-set of subjects will include up to approximately 30 AMPLEX subjects, allowing pharmacokinetic evaluation in at least 20 AMPLEX subjects. Both genders will be represented. Blood samples will be collected and processed to plasma for laboratory evaluation (plasma B2A concentration).

### **3.4.5 Withdrawal Criteria**

A study subject will be discontinued from participation in the study if:

- The Investigator feels that the subject can no longer fully comply with the requirements of the study or if any of the study procedures would not be in the best interest of the subject.
- The subject is lost to follow up. A subject will be considered “lost to follow-up” and terminated from the study when all of the following criteria have been met:
  - Failure to complete the remainder of the scheduled study visits without due cause; and
  - Documentation of three unsuccessful attempts to contact the subject via telephone and by certified mail.
- The subject wishes to withdraw their consent for participation in the study.

